### 4.0 BACKGROUND AND RATIONALE

***Influenza virus diversity*** Influenza A viruses are antigenically distinguished and classified by subtypes of haemagglutinin (HA) and neuraminidase (NA) with 16 HA and 9 NA subtypes identified within the natural reservoir of aquatic birds. The HA and NA surface antigens of influenza A virus are responsible for virus attachment and release from host cell receptors and are targeted by host antibodies. The HA is the major component of influenza vaccines and is subject to mutations resulting in antigenic drift that enables the virus to escape immune recognition.

In the northern hemisphere influenza is characterised by the occurrence of annual outbreaks during winter and worldwide pandemics, which have occurred at 11-52 year intervals during the past 300 years. Pandemics inflict huge socio-economic costs. The 1918-19 pandemic caused an estimated 40-100 million deaths globally. Pandemic influenza results from the emergence of an influenza A virus possessing a 'new' HA (antigenic 'shift') to which the population possesses little or no immunity and which is capable of spreading with a high attack rate in all parts of the world. Despite this viral diversity, only three HAs and two NAs have established human lineages during the last 100 yrs. In 1918, (Spanish flu: A/H1N1), 1957 (Asian flu: A/H2N2), 1968 (Hong Kong flu: A/H3N2) and 1977 (A/H1N1) strains emerged to cause widespread human infections.

Reasons for decline and emergence of dominant subtypes is unclear, although it seems likely that during interpandemic intervals, population immunity broadens to a point where the prevalent strain loses its capacity for further drift capable of eluding host defences.

***Swine influenza in humans*** Influenza as a disease of pigs was first described during 1918 when outbreaks of respiratory disease occurred simultaneously in humans and swine-herds living and working in close proximity. Pigs are thought to have an important role in inter-species transmission as they possess receptors in their respiratory tract capable of binding both avian and human influenza. Consequently they have been proposed as a possible mixing vessel in which novel reassortant viruses of pandemic potential may be generated. Occasional isolation of swine influenza viruses from humans with respiratory illness has confirmed that sporadic human infection can

occur. Generally, cases have been limited to laboratory workers or those with occupational swine exposure. However, a pandemic alert was raised in 1976 when swine H1N1 caused an outbreak of respiratory illness with one fatality among 13 soldiers at a military base in Fort Dix, New Jersey, USA. No exposure to pigs was found and sero-epidemiological investigation identified up to 230 further soldiers had been infected suggesting human-to-human transmission. Mass vaccination of the US public was initiated and halted amid reports of adverse vaccine reactions, media scepticism and the lack of pandemic activity.

***Pandemic A/H1N1 emergence in 2009*** In April 2009, near the end of the usual influenza season in the Northern Hemisphere, the first two cases of swine origin H1N1 influenza virus were identified in the United States. The CDC confirmed that these cases were caused by a genetically similar swine virus that had not been previously identified in the United States. Genetic analysis of the strains showed that they were derived from a new reassortment of six gene segments from the known triple reassortant swine virus, and two gene segments (NA and matrix protein) from the Eurasian influenza A (H1N1) swine virus lineage. Effectively all isolates are susceptible to neuraminidase inhibitors, but resistant to M2 inhibitors. The World Health Organization raised its pandemic alert level to Level 6 on June 11 2009, reflecting community level outbreaks of novel H1N1 infection in at least two different WHO regions and the onset of a new pandemic. H1N1 virus has reached over 170 countries and territories worldwide as of August 6 2009, causing at least 177457 cases and 1462 deaths. In the UK, the first pandemic wave is waning, but a substantial increase in cases of novel H1N1 infection is expected following the re-opening of schools in September.

***Burden of H1N1 disease, hospitalisations and admissions to ITU*** As of August 7, analysis of the distribution by age of 8974 individual case reports of influenza A(H1N1)v infection in 27 EU/EEA countries reveal that the age-distribution of non-hospitalised cases of H1N1 influenza is highest in the 10-19 year age group, followed by 0-9 and 20-29 year age groups. The age-distribution of hospitalised cases is significantly higher in the 20-29 year age group than in the under 20's. Estimates of transmissibility ( $R_0$  1.4-1.6) are significantly higher than observed in seasonal influenza and comparable to previous pandemics. In England, admission rates have been highest in the under 5's, but life-threatening complications requiring admissions to ITU increase with age and presence of 'high-risk' co-morbidity. It is unclear whether the higher prevalence of infection in the under 30's is related primarily to social mixing, cross-reacting antibodies that are more prevalent with increasing age, or both.

Preliminary studies in the United States have shown that cross-reactive microneutralisation (MN) antibody titres of  $\geq 160$  to A/California/2009 H1N1 were detected in 6% of adults aged 18 to 40 years, 9% of adults 18 to 64 years, and 33% of adults aged 60 years and older. After vaccination with seasonal vaccine, 7% of adults aged 18 to 40 years, 25% of adults aged 18 to 64 years, and 43% of adults aged 60 years and older had post-vaccination titres of  $\geq 160$ .

Infection with the current influenza H1 pandemic virus is mostly mild, with no increase in mortality above threshold national statistics the United States, despite widespread infection. The observed age distribution is unusual and different from seasonal influenza, being skewed towards younger age groups, resulting in deaths and ITU admissions in people who are normally affected less frequently.

Currently it is difficult to be certain about the impact of novel H1N1 infection on hospitalisation rates. A rate of 11% has been observed in the United States, but this is likely to be an overestimate due to the mild nature of the disease in many cases, and differences in clinical practice. An overall rate for Europe is around 5%-6%, but this too may be an overestimate due to the practice in some countries of admitting patients for isolation to control spread, rather than for severity of illness. In the UK, the observed rate has been around 1-2%.

**Current seasonal influenza vaccines** Inactivated influenza virus vaccines represent the mainstay of efforts to prevent influenza and its complications. Current licenced vaccines are produced from virus grown in eggs or cell culture systems and consist of either whole-virus, detergent-treated 'split-product', or purified HA and NA (subunit) surface antigen formulations.

Vaccine efficacy of 70-95% in healthy adults is obtained when there is a good match between the vaccine and the circulating strains. They display reduced efficacy against antigenically drifted viruses and are considered ineffective against unrelated subtypes.

The use of mammalian cell lines, notably Vero and MDCK cells, to grow influenza virus are approved substrates for production of licenced trivalent seasonal vaccines which may allow for increased vaccine production at short notice to meet unexpected demand.

As vaccine responses are generally lower in elderly subjects, efforts to improve immunogenicity have been investigated. The addition of MF59, a squalene-containing oil-in-water emulsion adjuvant, has been shown to increase post vaccination antibody titres and seroconversion rates in elderly and immunocompromised subjects. MF59-adjuvanted seasonal influenza vaccines have been licenced for clinical use since 1997. More recently, two other squalene-containing oil-in-water adjuvants have been developed by GSK and Sanofi. The GSK AS03 oil-in-water adjuvant has been extensively evaluated in association with H5N1 antigens.

**Global manufacturing capacity for pandemic influenza vaccine** Seasonal influenza vaccines are given at doses of 15µg HA per virus strain. The global human population is estimated at 6.77 billion. The annual global vaccine manufacturing capacity for trivalent seasonal influenza vaccines was 852 million doses in May 2009. Assuming that the yield of H1N1(v) antigen is comparable to that for seasonal virus strains, the present manufacturing capacity equates to 2.56 billion doses of monovalent H1N1(v) vaccine containing 15µg HA per dose. This would be enough for only 2.56 billion people if two doses containing 7.5µg HA were immunogenic, but could protect more people if one dose was sufficient in older people. Pandemic H1N1(v) vaccines will be supplied over a period of 6 months or more, so it is essential that dose sparing formulations and regimens are identified and deployed rapidly to protect as many vulnerable people as possible.

**Experience of pandemic and mock pandemic vaccines since the 1970's** Historically, influenza vaccines were first developed as 'whole virus' formulations. During the late 1970's whole virus vaccines were replaced by 'split', and highly purified 'surface antigen' formulations that caused fewer local and systemic reactions than whole virus vaccine, but are equally immunogenic when given to primed individuals as 'seasonal' or 'interpandemic' vaccine.

**Experience with H1N1 vaccines during the 1970's** Experience in unprimed individuals with vaccines produced from Hsw1N1 viruses (A/New Jersey/8/76) or H1N1 viruses (A/USSR/90/77) indicated that

high concentrations of antigen (>50µg HA) were needed in a single vaccine dose to generate HI titres that met the current European licensing criteria. In a two-dose schedule, HI titres  $\geq 40$  could be achieved with two doses containing 5µg HA. Overall, whole virus vaccines were more immunogenic than split or subunit vaccines. The split and surface antigen vaccine formulations were notably less immunogenic than whole virus vaccine when given to children, both during 1976 when influenza A/New Jersey/76 (H1N1) posed a pandemic threat, and during 1977 when A/USSR/77 (H1N1) virus re-emerged.

**European licensing criteria** During the late 1970's, influenza vaccines were poorly standardised. Subsequently, improved methods of measuring vaccine potency and ensuring vaccine standardisation were introduced, and in Europe, by criteria for licensure of seasonal, and latterly pandemic vaccines.

As specified in the Committee for Medicinal Products for Human Use (CHMP) 'Guidelines on dossier structure and content for pandemic influenza vaccine marketing authorisation application', it is anticipated that a pandemic candidate vaccine should at least be able to elicit sufficient immunological responses to meet and preferably exceed all three of the current standards set for existing vaccines in unprimed adults or elderly subjects as specified for seasonal vaccines.

These include assessments of the mean geometric increase in antibody titre (the seroconversion factor), the number of seroconversions or significant increases in antibody, and the seroprotection rate (i.e., the proportion attaining 'protective' levels of antibody). The criteria are based on the HI assay or single radial haemolysis. Both assays have been established as surrogates for protection.

The CHMP guidelines stipulate that vaccines should be tested in adults (18-60 yrs) and elderly (>60 yrs), in groups of >50 subjects, and attain the following:

*Adults (18-60 yrs):*

1. Seroconversions/ or significant rises (i.e., a 4-fold increase in post-vaccination titre ) by > 40%
2. Mean fold increase in GMT post-vaccination >2.5
3. Significant levels of antibody (i.e., having post-vaccination HI titres >1:40) in >70%.

*Elderly (>60 yrs):*

1. Seroconversions/ or significant rises (i.e., a 4-fold increase in post-vaccination titre) by > 30%
2. Mean fold increase in GMT >2
3. Significant levels of antibody (i.e., having post-vaccination HI titres >1:40) in >60%.

**Immunogenicity of plain (i.e., non-adjuvanted split and subunit avian influenza vaccines** As outlined below, neither split nor subunit vaccine formulations of H5, H7, and H9 avian influenza satisfy all three CHMP licensing criteria when given at doses of up to 90µg HA.

Treanor *et al.* showed that neither two 90µg doses of plain (i.e., non-adjuvanted) recombinant, baculovirus-expressed, H5 HA nor two 90µg doses of egg-grown, plain, inactivated, subvirion influenza A/Vietnam/1203/2004 (H5N1) vaccine satisfied the CHMP regulatory criteria. Nicholson *et al.* showed that two doses of all three 7.5-30µg formulations of plain A/Duck/Singapore/97 (H5N3) surface antigen vaccine failed to meet the CHMP criteria.

Bresson *et al.* showed that two doses of all three 7.5-30µg HA formulations of plain, split virus, A/Vietnam/1194/2004 (H5N1) vaccine satisfied the CHMP criterion for a greater than 2.5-fold increase in antibody titre, but 47% vaccinees failed to achieve protective levels of antibody after a second dose. Nolan *et al.* evaluated two doses of split A/Vietnam/1194/2004 (H5N1) vaccine containing 7.5-45µg HA with and without alum adjuvant. All formulations met the CPMP criterion for a greater than 2.5-fold increase in HI antibody titres after the second dose, but not the criterion for greater than 70% of participants achieving sero-protection.

Keitel *et al.* evaluated subvirion inactivated influenza A/H5N1 vaccine containing 3.75, 7.5, 15, or 45 µg of HA. Dose-related increases in antibody responses were noted after both vaccinations, but no formulation attained the CHMP criteria.

Stephenson *et al.* evaluated two 7.5, 15 and 30µg doses of plain, subunit, influenza A/Hong Kong/1073/99 (H9N2) vaccines in people before and after their 32nd birthday. The CHMP criterion for a greater than 2.5-fold increase in HI antibody titres was met after the second dose, but 86% vaccinees failed to attain protective levels of antibody. Cox *et al.* evaluated two doses of split H7N1 virus vaccine containing 12µg or 24µg HA. Neither formulation fulfilled the CHMP licensing criteria.

#### ***Immunogenicity of whole virus vaccines and vaccines adjuvanted with oil-in-water emulsions***

Whole virus vaccines and vaccines adjuvanted with oil-in-water emulsion are more immunogenic in man than split and subunit vaccines.

Lin *et al.* showed that a two-dose regimen of an aluminium hydroxide adjuvanted whole virus A/Vietnam/1194/2004 (H5N1) vaccine containing 10µg HA met all CHMP regulatory requirements for annual licensing of seasonal influenza vaccine. Ehrlich *et al.* evaluated whole virus A/Vietnam/1203/2004 (H5N1) vaccine (manufacturer by Baxter Healthcare) at doses of 3.75µg, 7.5µg, 15µg or 30µg HA with alum adjuvant, and 7.5µg or 15µg without adjuvant. Maximum responses to the vaccine strain were obtained with formulations without alum adjuvant. When assessed by single radial haemolysis, the 7.5µg dose met all three CHMP licensing criteria. Two criteria were met when antibodies were measured by haemagglutination inhibition. The vaccine also induced a neutralizing immune response against clade 2 and 3 strains and results without alum adjuvant elicited significantly higher immune responses than those with alum.

A phase I randomised trial of subunit and whole virus A/Hong Kong/1073/99 (H9N2) vaccine, given in two doses containing doses of 7.5µg, 15µg, or 30µg HA, revealed the presence of cross-reacting antibodies in participants born before 1969 who were older than 32 years – this finding is comparable to the recent observation of an age-related presence of cross-reacting antibodies to A/California/2009 (H1N1v) in the United States. In participants older than 32 years, one dose of whole virus or subunit vaccine evoked antibody responses associated with protection. However, in people aged 32 years or younger, whole virus vaccine produced a significantly higher probability of seroconversion compared with subunit virus for this age group.

Nicholson *et al.* evaluated two doses of subunit A/Duck/Singapore/97 (H5N3) vaccine containing 3.75µg, 7.5µg, and 15µg HA with and without MF59 oil-in-water adjuvant. In this phase I randomised trial, the geometric mean titres of antibody, and seroconversion rates, were significantly higher with MF59 adjuvanted vaccine. After the second injection, all MF59-adjuvanted vaccine

doses met all three CHMP licensing criteria. Further studies showed improved antibody persistence with MF59 containing vaccine, improved immune responses to other clades of H5 virus, and significantly higher antibody responses on boosting.

Leroux-Roels *et al.* evaluated A/Vietnam/1194/2004 (H5N1) vaccine manufactured by GlaxoSmithKline at doses of 3.8µg, 7.5µg, 15µg and 30µg HA with and without its proprietary AS03 adjuvant. The adjuvanted formulations were significantly more immunogenic than the non-adjuvanted formulations at all antigen doses. At the lowest antigenic dose, immune responses for the adjuvanted vaccine against the vaccine strain met or exceeded all US Food and Drug administration and EU CHMP licensure criteria. Further research showed broad cross-clade immune responses at the lowest antigen dose (3.8µg) with adjuvant, but no cross-clade response in the non-adjuvanted group.

**Reproducibility of the serology assays for influenza** For research purposes and vaccine licensure, influenza vaccines are evaluated by clinical trials that assess immunogenicity by the presence of serum antibody. Collaborative studies have shown that the serology assays are highly variable between laboratories – with variability between laboratories for HI assays varying by up to 32-fold. This leads to difficulties in interpreting results from different manufacturers. At the 5th WHO Meeting on Evaluation of Pandemic Influenza Prototype Vaccines in Clinical Trials, 12-13 February 2009, WHO highlighted the need for standardised assays and internationally accepted antiserum standards.

**The H1N1v vaccines purchased by the Government** The UK Departments of Health have purchased pandemic vaccines from Baxter Healthcare and GlaxoSmithKline. The Baxter vaccine (trade name, Celvapan) is a plain (i.e., non-adjuvanted), whole virus, vero-cell-grown, influenza A (H1N1)v pandemic formulation, containing 7.5µg HA per 0.5mL dose. The GlaxoSmithKline vaccine (trade name, Pandemrix) is an AS03-adjuvanted, split-product, egg-grown, influenza A (H1N1)v formulation, containing 3.75µg HA and oil-in-water AS03 adjuvant composed of squalene, DL- $\alpha$ -tocopherol and polysorbate 80. The expectation is that the initial limited supplies of both vaccines will be prioritised for those deemed to a greatest risk, but eventually everyone will have access to either vaccine. To ensure that protection is provided as rapidly as possible, it is imperative that vaccine is used efficiently.

**Conclusions** The available evidence indicates that whole virus vaccines, and split and subunit vaccines that contain oil-in-water adjuvant, are more immunogenic for avian H5, H7, and H9 HAs, and A/New Jersey/76 (H5N1) and A/USSR/77 (H1N1) than split and surface antigen vaccines without adjuvant. They also offer the potential for broadened antibody responses that could be critical in the event of antigenic drift during the course of the pandemic. Vaccine is likely to be in short supply (vaccine production takes time and is subject to various rate-limiting factors) and demand will be high worldwide. The available antigen will therefore need to be given optimally with consideration being given to the logistics of vaccine administration, immune responses, and the frequency and nature of adverse clinical reactions.

There have been no head-to-head comparisons of avian vaccines manufactured by Baxter Healthcare and GSK. Due to variability of serological assays, there are uncertainties as to whether

one preparation offers advantages over the other in terms of dose sparing in ‘older’ people, and significantly more ‘seroconversions’ in the young.

## 5.0 STUDY OBJECTIVES:

### Primary:

1. To evaluate the immunogenicity of Baxter cell-culture, non-adjuvanted, whole virus H1N1 vaccine, and GSK AS03-adjuvanted, split H1N1 vaccine with respect to Committee of Human Medicinal Products (CHMP) and FDA licensing criteria.

### Secondary:

2. To identify whether one or two doses of vaccine are required to satisfy the licensing criteria,
3. To examine the short term reactogenicity of the vaccines,
4. To examine the kinetics of the antibody responses to vaccination,
5. To examine persistence of antibody at 6 months,  
AND if appropriate (i.e., an antigenic drift variant emerges prior to the 2010-2011 influenza season),
6. To evaluate the breadth of the antibody response to the antigenic variant.

## 6.0 OVERALL STUDY DESIGN

### 6.1 Overall study design

This observer-blind, multi-centre study will be performed at three study sites in England (Leicester, Nottingham, and Sheffield) in a study population of healthy male and female adults, or adults with stable chronic medical conditions. Six groups of 60 male and female adults will be stratified by age (18-44, 45-64, and 65 years and older):

Age	1st Vaccination Day 0	2 nd Vaccination Day 21	Subjects/ group	Antibody measurements
18-44	GSK vaccine	GSK vaccine	60	Immunogenicity endpoints: Days 0, 21, & 42  Antibody kinetics: Days 7, 14, 28, 35  Antibody persistence: 6 months  Breadth of antibody response (if applicable) Days 0, 21 for immunogenicity endpoints & Days 7, 14, 28 & 35 for kinetics
	Baxter vaccine	Baxter vaccine	60	
45-64	GSK vaccine	GSK vaccine	60	
	Baxter vaccine	Baxter vaccine	60	
≥65	GSK vaccine	GSK vaccine	60	
	Baxter vaccine	Baxter vaccine	60	

At least 360 subjects will be randomly allocated to receive two 7.5µg HA doses of cell culture plain (i.e., non-adjuvanted) whole virus A/California/2009 (H1N1) vaccine, or two doses of AS03-adjuvanted influenza A/California/2009 (H1N1) split virus vaccine containing 3.75µg HA by IM injection. A second dose of the same vaccine containing the same quantity of antigen as in the first dose will be administered by the same route 21 days later. Subjects will be observed for local and systemic reactions for 30 minutes after each immunisation and will be monitored for any reactions and other adverse events for 7 days after each immunisation.

Blood for immunogenicity studies will be obtained at day 0 (pre-immunisation), day 7 ( $\pm 1$  day), day 14 ( $\pm 2$  days), day 21 ( $\pm 2$  days), day 28 ( $\pm 2$  days), day 35 ( $\pm 3$  days), day 42 ( $\pm 3$  days) and day 180 ( $\pm 10$  days).

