#### TIME AND EVENTS TABLE

Study visit	1	2	3	4	5	6	7	8
	Days after the first vaccination							
Window (days)	0	( $\pm 1$ )	( $\pm 2$ )	( $\pm 2$ )	( $\pm 2$ )	( $\pm 3$ )	( $\pm 3$ )	( $\pm 10$ )
Study day	0	7	14	21	28	35	42	180
Informed consent	X							
Inclusion/exclusion criteria	X			X				
Medical/medication history	X							
Pregnancy test	X			X				
Blood sample – antibody studies	X	X	X	X	X	X	X	X
Vaccination	X			X				
Thermometer/Diary card	X			X				
Diary card training	X							
Diary card returned/review		X			X			
Reminder re unsolicited events	X	X	X	X	X	X	X	
Adverse events monitoring		X	X	X	X	X	X	X
Termination of study								X

Immunogenicity to influenza viruses will be evaluated by HI, MN, and possibly SRH responses.

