**Visit 2: Day 7 ( $\pm 1$ ): Serology and Diary Card review**

The following activities will be carried out on day 7 and recorded in the CRF:

1. Collect and review the 1st Immunisation Diary Card, including new medication/analgesia/antipyretics taken during the preceding week (concomitant medication).
2. Remind subject to notify study personnel immediately if the subject experiences a SAE.
3. Collect 10ml clotted blood for serology. Process blood and store serum.
4. Schedule the Day 14 visit.

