**Visit 3: Day 14 ( $\pm 2$ ): Serology**

The following activities will be carried out on day 14 and recorded in the CRF:

1. Collect 10ml clotted blood for serology. Process blood and store serum.
2. Remind subject to notify study personnel immediately if the subject experiences a SAE.
3. Schedule the Day 21 visit.

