### **Visit 8: Day 180 ( $\pm 10$ ): Study termination**

The following activities will be carried out on day 180 and recorded in the CRF:

1. Collect 10ml clotted blood for serology. Process blood and store serum.
2. Ensure Completion of all study termination CRFs.

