## **8.6 Documentation/reporting of adverse and other clinical events**

All study subjects will be observed for at least 30 minutes after a vaccination for evidence of immediate reactions in general and in particular for symptoms of allergic phenomena (such as rashes, itching, or other allergic manifestations). Each subject, or where applicable, the subject's legally acceptable representative(s) will be instructed to complete a diary card for 7 days following each administration, to describe local and systemic reactions and other selected indicators of reactogenicity. If a local and systemic reaction or fever (derived from measured oral temperatures  $\geq 38.0^{\circ}\text{C}$ ) continues beyond the 7-day period after a vaccination, it will also be recorded on the Adverse Events CRF. If the subject recovers on the last day, then this fact will be recorded on the Local and Systemic Reaction CRF. All AEs must be reported and documented. The period of observation for adverse events extends from the time the subject receives vaccination through until 3 weeks after vaccination.

All AEs necessitating a physician's visit or consultation and/or leading to premature study discontinuation and all SAEs will be collected throughout the entire study and data will be reconciled at study termination.

All adverse events, regardless of severity, will be monitored by the investigator until resolution. All subjects experiencing adverse events - whether considered associated with the use of the study

vaccine or not - must be monitored until symptoms subside and any abnormal laboratory values have returned to baseline, or until there is a satisfactory explanation for the changes observed, or until death, in which case a full pathologist's report should be supplied, if possible. All findings must be reported on an Adverse Events CRF and on the "Serious Adverse Event" form, if necessary, which is part of the investigator's study file. All findings in subjects experiencing adverse events must be reported also in the subject's medical records.

In addition, any event resulting in a subject's withdrawal from subsequent vaccinations or from follow-up should be reported according to the protocol instructions.

All SAEs which occur during the course of the trial, whether considered to be associated with the study vaccination or not, have to be reported **within 24 hours** by telephone or fax to either of the following:

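### The 7-day adverse event monitoring period in the synopsis and 6.1 contradicts the 3 weeks in 8.6, and the visit steps omit the adverse event enquiry that the schedule table marks

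*Protocol*

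**What the plan says.** **Observation period.** The Design paragraph of the synopsis and section 6.1 both say that subjects are "monitored for any reactions and other adverse events for 7 days after each immunisation". Section 8.6 says: "The period of observation for adverse events extends from the time the subject receives vaccination through until 3 weeks after vaccination". It then adds a second tier: "All AEs necessitating a physician's visit or consultation and/or leading to premature study discontinuation and all SAEs will be collected throughout the entire study", with reconciliation of the data at termination.

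**Schedule.** The time and events table appears in the synopsis and again within 6.1. Its row "Adverse events monitoring" is marked at Visits 2 to 8 (Days 7 to 180), without restriction by type of event. Its row "Reminder re unsolicited events" is marked at Visits 1 to 7.

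**Visit steps.** Section 8.1 lists what is done at each visit. The diary card is collected and reviewed at Visits 2 and 5. At Visits 3, 6 and 7 the only safety step is: "Remind subject to notify study personnel immediately if the subject experiences a SAE". Visit 4 checks same-day analgesic use, takes the temperature, gives the second dose and inspects the injection site. It does not ask about events since Day 7. Visit 8 has two steps, a blood sample and "Ensure Completion of all study termination CRFs".

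**Planned outputs.** Section 9.2.7, like the synopsis, plans interim summaries of solicited and unsolicited events for Days 0-6, 0-21, 21-27 and 21-41. Section 9.2.6 divides follow-up into three intervals, the last of which is everything after 7 days.

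**The concern.** Two statements of the same rule disagree. The 7-day sentence expressly includes adverse events other than reactions, so it cannot be read as describing only the diary week. If it governs, the planned summaries that run past the diary week have no basis.

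The second disagreement is between the table and the visit steps. Where the table has a reminder about unsolicited events, the steps for Visits 3, 6 and 7 have a reminder about serious events only. Staff who work from the visit list are not told to ask about non-serious events that began after the diary was handed in.

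An analysis plan cannot repair this later, because an event that nobody asked about leaves no record. The interim safety summaries are meant to inform national vaccination strategy, and uneven enquiry would make some sites' rates look lower than they are. Under the sequential allocation described in 7.4 (scenario B), which the protocol considers the likelier course, a drift in enquiry practice over time could also be mixed up with vaccine.

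**Working it through.** The protocol gives no figure on this point to reproduce. The check compares the passages and counts days.

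**1. Can each stated period supply the planned windows?** Inputs are the 7 days (synopsis, 6.1), the 3 weeks (8.6) and the windows in 9.2.7. I take the 7 days as Days 0-6 and Days 21-27, which matches the shorter windows in 9.2.7, and I apply the 3 weeks after each dose.

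- First dose, window Days 0-21: 22 days. Covered by the 7-day rule: Days 0-6, 7 days. Not covered: Days 7-21, 22 − 7 = 15 days; 15/22 = 68%.
- Second dose, window Days 21-41: 21 days. Covered by the 7-day rule: Days 21-27, 7 days. Not covered: Days 28-41, 21 − 7 = 14 days; 14/21 = 67%.
- If Days 7 and 28 are also counted as covered, the gaps become 14/22 = 64% and 13/21 = 62%.
- Under the 3-week rule both windows lie inside the observation period and the gap is zero.

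The analyses therefore fit 8.6 and do not fit the 7-day sentence.

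**2. If the 3-week rule governs, where would a non-serious event after the diary week be picked up?**

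| Visit (day) | Table: adverse event monitoring | 8.1 steps: general adverse event enquiry | What it serves |
|---|---|---|---|
| 2 (7) | marked | diary review | diary week, dose 1 |
| 3 (14) | marked | none; serious events reminder | Days 7-21 |
| 4 (21) | marked | none about the time since Day 7 | closes Days 0-21 |
| 5 (28) | marked | diary review | diary week, dose 2 |
| 6 (35) | marked | none; serious events reminder | Days 28-41 |
| 7 (42) | marked | none; serious events reminder | closes Days 21-41 |
| 8 (180) | marked | none | whole-study tier only |

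Four visits could capture the events that matter for the two windows: 3 and 4 after the first dose, 6 and 7 after the second. The table schedules monitoring at all four, and the steps of none of the four carry it out. For example, a new non-serious complaint starting on Day 10 has no listed step that would elicit it.

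**3. Visit 8.** It has no bearing on the Day 0-21 and 21-41 windows. It matters for the 8.6 tier that runs to study end: events leading to a medical consultation, events leading to discontinuation, and serious events. The Visit 8 steps contain no enquiry that serves this tier, and the table row does not show that the tier exists.

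**The case against.** The strongest reply is that the protocol already provides for collection beyond the diary week, and much of that reply stands.

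- The time and events table sits inside 6.1, so a site that follows all of 6.1 is scheduled to monitor adverse events at every visit from Day 7.
- Section 8.6 requires every adverse event to be reported and documented.
- Section 9.2.6.2 names 8.5 and 8.6 as the place where collection of unsolicited events is described, which favours the 3-week rule.
- Diaries ask for unsolicited symptoms and continue if symptoms persist (8.3). Reactions lasting past 7 days go on the adverse events form.
- The case report form pages are not shown and may prompt at each visit.

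Three stronger readings are therefore not supported. A reader might infer three rival periods of 7 days, 3 weeks and 180 days; but collection to Day 180 is a restricted tier that 8.6 states alongside the 3 weeks. A reader might infer that nothing is actively collected after the diary week, or that the planned summaries will lack data; the table and 8.6 say otherwise. A reader might infer that medically attended events from Day 42 to Day 180 have no means of collection; the table marks Visit 8 and 8.6 provides for reconciliation at termination, so only the 8.1 list leaves the step out.

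The reply does not remove the fault. The table and 8.6 are one side of the contradiction, with the 7-day sentence and the visit steps on the other, and the protocol does not say which a site should follow. Extending the diary for persisting symptoms does not reach an event that first appears after the card has been returned.

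**Conclusion.** The point holds as an internal contradiction with a practical consequence. The 7-day statement conflicts with 8.6 and with the planned analyses. Separately, five visits (3, 4, 6, 7 and 8) lack in 8.1 the enquiry that the table schedules.

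The exposure is to uneven capture across sites of non-serious events starting on Days 7-21 or 28-41, which are 68% and 67% of the two analysis windows. Those percentages measure time left open if a site follows the 7-day wording. They do not estimate the share of events that would be missed, and the protocol gives nothing from which to estimate it. The day counts assume that the 7 days include the day of vaccination and that the 3 weeks apply after each dose.

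Solicited reactions in the diary week are not affected. The correction should be made because a stated rule conflicts with planned safety outputs, but the documents do not show that data would be lost.

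**What to change.** 1. Reconcile the synopsis Design paragraph, 6.1, both copies of the time and events table and 8.6 to one tiered observation period that covers the windows analysed in 9.2.7.
2. Show the whole-study tier in the table, by a footnote or a separate row, so that the mark at Visit 8 states which events it refers to.
3. Add to the 8.1 steps for Visits 3, 4, 6 and 7 an instruction to ask about and record adverse events since the previous visit. Add to Visit 8 the corresponding enquiry for the whole-study tier. The table already schedules both.

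The cost is protocol wording and one question at each of five visits that take place anyway. Sample size, visit schedule and planned analyses do not change.
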